5.1.3 Other Agent (s): **MELITAC 12.1**

MELITAC 12.1 vaccine comprises 100 μ g each of the 12 melanoma peptides plus 190 μ g tetanus toxoid peptide (Peptide-tet). Peptides are synthesized under good manufacturing practice (GMP) conditions by PolyPeptide Group (San Diego, CA; formerly Multiple Peptide Systems), reconstituted, mixed, sterile-filtered, and vailed under GMP conditions by Merck (Germany). The 12-melanoma peptide mixture and tetanus peptide preparation are made as separate sterile aqueous solutions to be administered in an emulsion with Montanide ISA-51 VG adjuvant (1 mL), using the 2-syringe method after emulsion stability and quality is verified. MELITAC 12.1 stimulated immune responses with an excellent safety profile and with presumptive evidence of efficacy in the adjuvant setting.

At this writing, the 12-MP has been administered in combination with Peptide-tet and GM-CSF in Montanide ISA-51 VG adjuvant to more than 200 participants enrolled in 3 studies run through the University of Virginia Human Immune Therapy Center (HITC) in collaboration with other centers (Mel39, Mel43, E1602) [[[name] 2007](#); [[name] 2009](#); [[name] 2010](#)] and 12-MP has been administered in Montanide ISA-51 VG adjuvant, with or without Peptide-tet in about 300 participants (Mel43, Mel44, E1602) [[[name] 2010](#); [[name] 2011](#); [[name] 2009](#)]. No data are available regarding the distribution and excretion of the vaccine preparation. In vitro studies have indicated the half-life of synthetic peptides in the presence of serum peptidases is short (approximately 22 seconds) [[Brinckerhoff 1999](#)]. However, in vivo data describing the metabolism of the vaccine are not available.

In the first 51 participants vaccinated with the 12-MP and Peptide-tet with GM-CSF in Montanide ISA-51 VG adjuvant, the majority of toxicities described have been of minimal severity. The most frequent AEs for participants receiving the 12-MP in

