5.1.4 Other Modalities or Procedures: N/A

5.1.5 Investigational Imaging Agent Administration: N/A

5.2 **Definition of Dose-Limiting Toxicity:**

Dose-limiting toxicities (DLTs) include all Grade 3 AEs regardless of investigator attribution or relatedness except for those listed below.

Based on investigator determination the following Grade 3 toxicities can be deemed non-DLT:

- adverse event with a clear alternative explanation (e.g. due to disease progression)
- transient toxicities (≤ 72 hours)
- injection site reactions that are expected and do not require any surgical intervention or repair
- abnormal laboratory values without associated clinically significant signs or symptoms

There are two exceptions to the above. Grade 1 or greater ocular toxicities will be considered a DLT. Grade 2 LFT elevations will be considered a DLT.

In the event of a DLT, it will be determined by the safety team whether both the INCB024360 AND the MELITAC 12.1 will be permanently discontinued. In cases of vaccine injection site reaction or other vaccine related adverse events the INCB024360 may be continued if the vaccine related adverse event continues to show improvement. Management and dose modifications associated with the above adverse events are further outlined in [Section 6](#).

5.3 **General Concomitant Medication and Supportive Care Guidelines**

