5.4 Duration of Therapy

Patients with surgically incurable stage III or IV melanoma and tissue amenable to serial biopsy will receive the sequential therapy with INCB024360 alone for 3 weeks followed

by continued INCB024360 plus 6 MELITAC 12.1 vaccines administered intradermally or subcutaneously on days 21, 28, 35, 56, 77, and 98 (weeks 3, 4, 5, 8, 11, and 14).

Serial biopsies will be obtained up to 14 days before starting INCB024360, on day 21 (before the first vaccine), and on day 42 (a week after the third vaccine). When feasible a biopsy will be obtained at week 16 (2 weeks after the sixth vaccination). If possible, tumors will be biopsied from patients coming off study, including for progression of disease.

In the absence of treatment delays due to AE(s), treatment may continue for up to 3 additional cycles of INCB024360 (a total of 4 cycles) after consultation with the trial Principal Investigator, CTEP, and the CITN, or until one of the following criteria applies:

- Disease progression by Response Evaluation Criteria In Solid Tumors (RECIST) or Immune-Related Response Criteria (irRC)
- Intercurrent illness that prevents further administration of treatment
- Unacceptable AE(s)
- Patient decides to withdraw from the study
- General or specific changes in the patient's condition rendering the patient unacceptable for further treatment in the judgment of the investigator

If additional cycles of INCB024360 are deemed appropriate for the patient, the INCB024360 will be given without the administration of the MELITAC 12.1 vaccines.

Only the end of treatment biopsy will be obtained if additional cycles of INCB024360 are approved for each patient.

In patients who are approved to receive additional cycles of INCB024360, a reduced volume of blood will be drawn for specific assays. ([Study Calendar, footnote ***](#))

A delay of up to 60 days between treatment cycles will be allowed.

In the event of unexpected serious AEs related to either component of the combination, treatment of the affected participant with INCB024360 and/or MELITAC 12.1 will be discontinued after analysis by the DSMC, Incyte, and CITN.

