6. DOSING DELAYS/DOSE MODIFICATIONS

All toxicity associated with prior treatment must resolve to grade 1 or less off steroid treatment for at least 2 weeks. Patients who have discontinued treatment for pulmonary, renal or neurologic toxicity or who have experienced grade 4 toxicity should not be enrolled in the study.

All related toxicities will be reviewed by the protocol P.I., participating site P.I.s, CTEP and the CITN Coordinating Center for an indication to change the dosing schedule.

The selected doses of INCB024360 and MELITAC 12.1 have been established as having excellent safety profiles. Dose escalation is not planned or necessary. However, when used together, unexpected toxicities might occur. Thus, rules for stopping will be incorporated in the event that dose-limiting AEs are observed.

Toxicities for each agent will be monitored continuously and will be graded by the NCI CTCAE v4.0 with stopping rules for AEs. At the discretion of the investigators, treatment may be held for up to 14 days to permit the evaluation or resolution of symptoms that may be unrelated to treatment but may affect patient safety (e.g., influenza, minor trauma).

DLT's include all Grade 3 AEs regardless of investigator attribution or relatedness except for expected grade 3 injection site reactions. ([section 5.5](#))

Based on investigator determination the following Grade 3 toxicities can be deemed non-DLT:

- adverse event with a clear alternative explanation (e.g. due to disease progression)
- transient toxicities (≤ 72 hours)
- injection site reactions that are expected and do not require any surgical intervention or repair

- abnormal laboratory values without associated clinically significant signs or symptoms

There are two exceptions to the above: Grade 1 or greater ocular toxicities will be considered a DLT. Grade 2 LFT elevations will be considered a DLT.

In the event of a DLT, it will be determined by the safety team whether both the INCB024360 AND the MELITAC 12.1 will be permanently discontinued.

Vitiligo will not be considered a DLT.

Pages 33, 34 and 35 include tables for some of the more common AE's including instructions for handling. For any AE's not listed in these tables, proceed in the following manner:
Grade 1 and Grade 2: Continue to monitor, follow and grade these adverse events.
Grade 3: Stop Protocol Therapy including both INCB024360 and MELITAC 12.1
Grade 4: Stop Protocol Therapy including both INCB024360 and MELITAC 12.1

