In addition, treatment will be discontinued for (a) Any DLT, (b) disease progression requiring other therapy, (c) noncompliance with study requirements, (d) other safety considerations in the judgment of the investigator, or (e) patient request.

The treatment regimen will be considered safe as long as the number of participants experiencing a treatment-related AE (DLT) does not exceed 33%. If more than 33% of patients accrued are known to have experienced a treatment-related DLT, the study will be closed to further accrual, except that 1 treatment related DLT observed out of the first 3 patients accrued will be acceptable and will not result in the closing of the study.

Nausea	Management/Next Dose for INCB024360	Management/Next Dose for MELITAC 12.1
≤ Grade 1	No change in dose	No change in dose
Grade 2	No change in dose	No change in dose
Grade 3	Off Protocol Therapy	Off Protocol Therapy
Grade 4	Off protocol therapy	Off protocol therapy
Recommended management: antiemetics		

Vomiting	Management/Next Dose for INCB024360	Management/Next Dose for MELITAC 12.1
≤ Grade 1	No change in dose	No change in dose
Grade 2	No change in dose	No change in dose
Grade 3	Off Protocol Therapy	Off Protocol Therapy
Grade 4	Off protocol therapy	Off protocol therapy
Recommended management: antiemetics		

Investigations (Liver Function Tests ALT + AST)	Management/Next Dose for INCB024360	Management/Next Dose for MELITAC 12.1
< Grade 1	No change in dose	No change in dose
Grade 1*	No change in dose	No change in dose

Investigations (Liver Function Tests ALT + AST)	Management/Next Dose for INCB024360	Management/Next Dose for MELITAC 12.1
Grade 2	Off Protocol Therapy	Off Protocol Therapy
Grade 3 or 4	Off Protocol Therapy	Off Protocol Therapy
*For Grade 1 LFT Elevations, increase LFT monitoring to twice weekly.		

Diarrhea	Management/Next Dose for INCB024360	Management/Next Dose for MELITAC 12.1
≤ Grade 1	No change in dose	No change in dose
Grade 2	No change in dose	No change in dose
Grade 3	Off Protocol Therapy	Off Protocol Therapy
Grade 4	Off protocol therapy	Off protocol therapy
Recommended management: physician discretion		

Neutropenia	Management/Next Dose for INCB024360	Management/Next Dose for MELITAC 12.1
≤ Grade 1	No change in dose	No change in dose
Grade 2	No change in dose	No change in dose
Grade 3	Off Protocol Therapy	Off Protocol Therapy
Grade 4	Off protocol therapy	Off protocol therapy
Recommended management: treatment of infection as appropriate		

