Thrombocytopenia	Management/Next Dose for INCB024360	Management/Next Dose for MELITAC 12.1
≤ Grade 1	No change in dose	No change in dose
Grade 2	No change in dose	No change in dose
Grade 3	Off protocol therapy	Off protocol therapy
Grade 4	Off protocol therapy	Off protocol therapy
Recommended management: platelet transfusions if indicated		

Fatigue	Management/Next Dose for INCB024360	Management/Next Dose for MELITAC 12.1
≤ Grade 1	No change in dose	No change in dose
Grade 2	No change in dose	No change in dose
Grade 3 or Grade 4	Off Protocol Therapy	Off Protocol Therapy
Recommended management: physician discretion		

Ocular Toxicity	Management/Next Dose for INCB024360	Management/Next Dose for MELITAC 12.1
≤ Grade 1	Off protocol therapy*	Off protocol therapy
Grade 2	Off protocol therapy	Off protocol therapy
Grade 3	Off protocol therapy	Off protocol therapy
Grade 4	Off protocol therapy	Off protocol therapy
*Defined as treatment-related grade 1 ocular toxicities		

Chills/fever/malaise following immunization	Management/Next Dose for INCB024360	Management/Next Dose for MELITAC 12.1
≤ Grade 1	No change in dose	No change in dose
Grade 2	No change in dose	No change in dose
Grade 3	Off protocol therapy if fails to resolve by the next scheduled immunization	Off protocol therapy if fails to resolve by the next scheduled immunization
Grade 4	Off protocol therapy	Off protocol therapy

Injection site reaction	Management/Next Dose for INCB024360	Management/Next Dose for MELITAC 12.1
≤ Grade 1	No change in dose	No change in dose
Grade 2	No change in dose	No change in dose
Grade 3	No change in dose*	No change in dose**
Grade 4	Off protocol therapy	Off protocol therapy

*See section 5.2

** MELITAC 12.1 vaccine may be given if the grade 3 injection site reaction combined area of skin ulceration is <2 cm

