7.1.3 CAEPRs for MELITAC 12.1

7.1.3.1 12-MP and Peptide-tet vaccine

There is no reason to expect direct toxicity of the melanoma peptides, as they are not directly cytotoxic in vitro. On the other hand, because some of these peptides are identical or similar to a portion of a normal protein, risks of autoimmunity in humans are important to evaluate. Because no murine system adequately models the human immune response to these peptides, the most meaningful evaluation of this peptide vaccine mixture is in participants with melanoma. We will focus this study on participants with advanced melanoma (i.e., unresectable stage III or stage IV melanoma). These individuals face a high risk (>90%) of premature death, and the anticipated risk of short-term or long-term toxicity of this vaccine preparation is minimal ([Table 7.1.4.1](#)), although it might delay or decrease the risk of morbidity and mortality due to melanoma in these participants. The potential implications of autoimmunity against cells of melanocytic lineage are illustrated by reported cases of vitiligo occurring coincident with regressions of melanoma. Most of these are limited, often occurring in skin surrounding the regressing melanoma, but occasionally occurring systemically. While pathogenesis of this phenomenon can only be hypothesized, it is reasonable to consider this a worst-case scenario.

****All participants should be closely observed for AEs for at least 20 minutes after each vaccination. Any time thereafter, participants should report any AEs to their treating physician.**

Table 7.1.4.1. Toxicity Data for Mel 39 (Arm B) and Mel 43 (Arms B and D)

Description	N	%	Grade, n		
			1	2	3
Overall number of Participants	51	100	1	35	15
Allergy/Immunology	6	12	5	1	.
Allergic rhinitis	4	8	3	1	.
Autoimmune reaction	2	4	2	.	.
Blood/Bone Marrow	8	16	7	1	.
Hemoglobin	4	8	4	.	.
Hemoglobin	2	4	2	.	.
Lymphopenia	2	4	1	1	.
Cardiovascular (General)	2	4	2	.	.
Edema	2	4	2	.	.
Constitutional Symptoms	43	84	27	12	4
Constitutional symptoms, other	1	2	1	.	.
Fatigue (lethargy, malaise, asthenia)	42	82	27	11	4
Fever (in the absence of neutropenia)	14	27	11	3	.
Rigors, chills	27	53	25	2	.
Sweating (diaphoresis)	16	31	16	.	.
Dermatology/Skin	51	100	3	35	13
Alopecia	1	2	1	.	.
Bruising	1	2	1	.	.
Dermatology/Skin, other	4	8	3	1	.
Flushing	10	20	10	.	.

Description	N	%	Grade, n		
			1	2	3
Hand-foot syndrome	1	2	1	.	.
Injection site reaction	51	100	3	35	13
Pigmentation changes (e.g., vitiligo)	1	2	1	.	.

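### Section 6 stops treatment for any DLT, but its Grade 3 chills/fever/malaise row can keep both agents going after one, and the safety team's discretion is not reconciled with the stop

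*Combined protocol and SAP*

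**What the plan says.** **General stop.** Section 6, just before the event tables: "In addition, treatment will be discontinued for (a) Any DLT". The same list contains progression, noncompliance, other safety considerations and patient request. No exception is given.

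**Safety team.** Sections 5.2 and 6 both say that after a DLT "it will be determined by the safety team whether both the INCB024360 AND the MELITAC 12.1 will be permanently discontinued". Section 5.2 adds that, for injection-site and other vaccine-related events, "the INCB024360 may be continued if the vaccine related adverse event continues to show improvement".

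**DLT definition.** Sections 5.2 and 6 count all Grade 3 events regardless of attribution. The investigator may deem some non-DLT: those with a clear alternative cause, those lasting 72 hours or less, expected injection-site reactions needing no surgical repair, and laboratory values without clinically significant signs or symptoms. Ocular toxicity of any grade and Grade 2 LFT elevations are DLTs.

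**The row.** For Grade 3 chills, fever or malaise after immunization, both columns read: "Off protocol therapy if fails to resolve by the next scheduled immunization".

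**Other removal routes.** Section 5.4 says that after an unexpected serious related event, "treatment of the affected participant with INCB024360 and/or MELITAC 12.1 will be discontinued after analysis by the DSMC, Incyte, and CITN". It also lists unacceptable adverse events among the reasons treatment ends, and Section 5.6 removes patients who meet a Section 5.4 criterion. Section 5.5 defines unacceptable toxicity to include any unexpected Grade 3 or higher event, and vaccination events needing antibiotics, debridement or narcotics.

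**The concern.** This is a novel combination, and Section 6 itself warns that unexpected toxicities might occur when the agents are used together. The instruction for a patient with a DLT should therefore read the same wherever a clinician looks. Here the general text takes the patient off treatment, while the table for one class of vaccine reaction keeps both agents going if the event clears in time. A site working from the table could revaccinate a patient whom the general text has already taken off. The safety-team sentence raises a second question: is the stop automatic, or does it await a decision? Section 5.2 refers the reader to Section 6 for management, but Section 6 contains both the mandatory and the discretionary statement.

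**Working it through.** The plan gives no figure on this point, so the check compares the rules and does some simple date arithmetic.

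**1. When the row and the DLT definition disagree**

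Inputs: vaccine days 21, 28, 35, 56, 77 and 98 (Section 5.1) and the 72-hour (3-day) limit (Section 5.2).

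| After vaccine | Days to next vaccine | Minus 3 days |
|---|---|---|
| 1 | 28 − 21 = 7 | 4 |
| 2 | 35 − 28 = 7 | 4 |
| 3 | 56 − 35 = 21 | 18 |
| 4 | 77 − 56 = 21 | 18 |
| 5 | 98 − 77 = 21 | 18 |
| 6 | none | no limit set |

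These are maximum windows, assuming onset on the vaccination day and visits on schedule. A Grade 3 event lasting more than 3 days and resolving within 7 days (vaccines 1–2) or 21 days (vaccines 3–5) is outside the duration exception. Unless another exception applies it is a DLT, and the row does not stop either agent. After vaccine 6 the row has no end point. That matters only for a patient still taking INCB024360 or going on to the further cycles that Section 5.4 allows.

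**2. How the other tables behave**

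Ten event tables are given. At Grade 3, both agents come off for nausea, vomiting, LFT, diarrhea, neutropenia, thrombocytopenia, fatigue and ocular toxicity: 8 of 10. The remaining two are injection-site reaction, where expected reactions needing no repair may be excepted from DLT status, and chills/fever/malaise. The LFT table takes both agents off from Grade 2, so that DLT has no gap.

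**3. How often the row might matter**

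Table 7.1.4.1 covers 51 vaccinated patients without INCB024360. Section 5.1.3 describes 51 participants who also received GM-CSF, apparently the same group; GM-CSF is not used here. Exact two-sided 95% intervals:

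- Grade 3 fever 0/51 and Grade 3 chills 0/51: upper bound 1 − 0.025^(1/51) = 7.0% each.
- The combined category "Fatigue (lethargy, malaise, asthenia"): Grade 3 in 4/51 = 7.8% (2.2% to 18.9%). The malaise share is not given, so Grade 3 malaise lies between 0 and 7.8% in those data.

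Durations are not given. Section 5.3.2 says that the other common vaccine toxicities were evident for approximately 24 hours, so events over 72 hours should be a minority. Post-vaccine malaise could also be handled under the fatigue table, which stops both agents at Grade 3, so the same event has two possible answers.

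**4. The safety-team sentence beside the general stop**

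One text says treatment is discontinued for any DLT. The other says a team determines whether both agents are permanently discontinued, and Section 5.2 lets INCB024360 continue in one case. No sentence orders these. Section 6 ranks its tables only against the default grade rule for events not listed, not against the any-DLT stop.

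**The case against.** The strongest reply is that the texts can be reconciled. The any-DLT stop opens with words that make it cumulative with the other instructions, so it can apply on top of the row, which nowhere says that a patient with a DLT may continue. The safety-team sentence can be read as deciding only permanence and scope (one agent or both), with the INCB024360 allowance as a specific exception. Section 6 also sends all related toxicities to joint review by the protocol and site investigators, CTEP and the Coordinating Center, which limits divergence between sites.

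Much of this stands. The cumulative reading is available, and Sections 5.4 to 5.6 give a further stop for unexpected Grade 3 or higher toxicity and for vaccine-site events needing antibiotics, debridement or narcotics. But the protocol does not state the permanence-or-scope reading, and a clinician using the row would not see that a separate stop applies. Sections 5.4 to 5.6 close the row's gap only if the event is judged unexpected, and the protocol gives chills, fever and malaise their own row as anticipated reactions.

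A reader might also infer that about 8% of patients, or up to 17% for injection-site reactions, are left to open discretion, using the Mel44 rates in Section 5.3.2 (8% unexpected Grade 3 related events; 10% ulceration plus 7% induration). The documents do not support this. Unexpected Grade 3 events are the class that Section 5.5 already treats as unacceptable. Section 5.3.2 calls the injection-site reactions expected and not dose-limiting, and Section 5.5 says that ulceration over 2 cm takes the patient off study without being a DLT.

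**Conclusion.** The inconsistency is real but narrow. As written, the Grade 3 chills/fever/malaise row can keep both agents going after an event that the protocol defines as a DLT, for up to 4 days (vaccines 1–2) or 18 days (vaccines 3–5) beyond the 72-hour limit, followed by revaccination. The safety-team sentence lacks a statement of how it relates to the any-DLT stop.

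This rests on no other Section 5.2 exception applying and on the event not being judged unexpected under Section 5.5. Affected patients should be few, given 0 of 51 for Grade 3 fever and for Grade 3 chills. That is only a guide, because those patients did not receive INCB024360.

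It would be wrong to infer that study-level stopping is affected. The closing rule (more than 33% with treatment-related DLTs) counts DLTs whether or not dosing continued. The point concerns instructions for the individual patient and merits a clarifying correction.

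**What to change.** 1. In the Grade 3 chills/fever/malaise row, both columns, add the DLT condition. Suggested wording: *Off protocol therapy if the event meets the DLT definition in Section 5.2, or is unresolved when the next immunization is due.* This keeps every Section 5.2 exception and also covers vaccine 6.
2. In Sections 5.2 and 6, state that any DLT stops both agents at once. The safety team may then decide only whether INCB024360 alone continues or resumes after an improving vaccine-related event. That option would be closed if the event is an unacceptable toxicity under Section 5.5, or an ocular or Grade 2 or higher LFT DLT.
3. Cross-reference this rule in Section 5.4 and in the row.

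The cost is a protocol amendment, with no new visits or data. An occasional patient will stop earlier, and one who stops after vaccines 1 to 3 may miss the day 42 biopsy that serves Objective 2. The mandatory day 21 biopsy is taken before the first vaccine and is kept.

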Patients will receive 3 weeks of INCB024360, followed by continued INCB024360 plus 6 vaccinations with MELITAC 12.1. Patients who have disease progression while receiving anti-PD1 or anti-PDL-1 antibody treatment will be allowed to enroll and receive INCB024360 within 2-6 weeks of last antibody treatment administration. Patients enrolled within the 6 week window will be enrolled in Cohort B and administered INCB024360 orally at a dose of 100 mg twice daily continuously up to day 98 (3 months) plus vaccines. Patients who enroll in the study after confirmed disease progression on anti-PD1/PDL-1 after 6 weeks of receiving the last dose of antibody will be enrolled in Cohort A and receive 300 mg BID of INCB024360 plus vaccines.

Patients that show response at 3 months will be considered for additional INCB024360.

As a lead-in to ensure safety and tolerability of the combination of INCB024360 and MELITAC 12.1, the first 3 patients enrolled in the study will be at the dose of 300 mg bid staggering each patient's enrollment by at least 2 weeks so that the first patient will receive 2 doses of the vaccine in combination with INCB024360 before the second patient starts the combination of agents. Enrollment will be halted after the first 3 patients are enrolled to allow for observation of any toxicity before opening further enrollment. The next nine patients will receive either 300 mg bid of INCB024360 or 100 mg bid ([Table 5.1](#)). For patient safety, if a Dose Limiting Toxicity (DLT) occurs in the first three patients treated at the 300 mg BID dose level of INCB024360 + MELITAC 12.1 vaccine, the subsequent 9 patients will be treated with the dose of either 300 mg BID or 100 mg of INCB024360 + MELITAC 12.1. If two DLTs occur in the first 6 patients treated at the

300 mg dose of INCB024360 + MELITAC 12.1 the study will be stopped.

Treatment will be administered on an outpatient basis. Reported AEs and potential risks are described in [Section 7](#). Appropriate dose modifications are described in [Section 6](#). No investigational or commercial agents or therapies other than those described below may be administered with the intent to treat the patient's malignancy. The patient will be requested to maintain a medication diary of each dose of medication. The medication diary will be returned to clinic staff at the end of each course.

[Table 5.1. Agent Administration and Timing of Assessments](#)

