13.3 Sample Size/Accrual Rate

The study plans to enroll a total of 12 patients at 3 or 4 clinical research sites. Each patient will act as their own control. Patients without adequate sampling for immune responses will be replaced.

Accrual rate of patients is expected to be approximately 3 patients per month.

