13.4 Stratification Factors - None

13.5 Analysis of Secondary Endpoints

- 13.5.1 To determine whether a regimen of INCB024360 that normalizes serum Kyn/Trp ratios plus MELITAC 12.1 vaccine changes the level or character of the vaccine-induced CD8+ and CD4+ specific T-cell immune responses as measured in peripheral blood, as compared to prior published experience.
- 13.5.2 To evaluate the extent to which INCB024360 plus MELITAC 12.1 vaccine alters the number and character of PBMC populations, including T and NK cells, as evaluated by multiparameter flow cytometry.
- 13.5.3 To evaluate the extent to which INCB024360 plus MELITAC 12.1 vaccine alters the PBMC transcriptome.
- 13.5.4 To assess the safety and tolerability of INCB024360 plus MELITAC 12.1 vaccine.
- 13.5.5 To obtain preliminary data on the tumor response rate of INCB024360 plus MELITAC 12.1 vaccine by ORR, time to tumor progression, and overall survival.
- 13.5.6 To associate any observed changes with the expression of IDO1 protein by IHC in tumor or tumor-infiltrating cells.

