13.6 Reporting and Exclusions

13.6.1 Evaluation of Toxicity

All patients will be evaluable for toxicity from the time of their first treatment with INCB024360.

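### Section 6 uses one 33% DLT threshold both to close accrual and to call the regimen safe; with 12 patients, not crossing it does not show safety

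*Combined protocol and SAP*

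**What the plan says.** Section 6 (Dosing Delays/Dose Modifications) gives two consecutive statements built on one number. The first is a judgement on the regimen: "The treatment regimen will be considered safe as long as the number of participants experiencing a treatment-related AE (DLT) does not exceed 33" percent. The second is an accrual rule: "If more than 33% of patients accrued are known to have experienced a treatment-related DLT, the study will be closed to further accrual", with the exception that "1 treatment related DLT observed out of the first 3 patients accrued will be acceptable".

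Section 5.1 adds a separate study-level rule. It begins "If two DLTs occur in the first 6 patients treated at the" 300 mg dose, and its consequence is that the study stops.

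On size, Section 13.3 says: "The study plans to enroll a total of 12 patients at 3 or 4 clinical research sites". It also says: "Patients without adequate sampling for immune responses will be replaced". Section 13.2 justifies twelve patients by the CD8+ endpoint, not by toxicity. Section 13.6.1 sets the toxicity population: "All patients will be evaluable for toxicity from the time of their first treatment with INCB024360".

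On analysis, Section 13.5.4 restates the objective, "To assess the safety and tolerability of INCB024360 plus MELITAC 12.1 vaccine", and adds no method. Section 5.6 says that safety is evaluated by recording treatment-related adverse events, and Section 11 names CTCAE v4.0. The only confidence interval mentioned in Section 13 is in 13.6.2, on tumor response. No acceptable true DLT rate, confidence level or error probability is given for the 33% threshold.

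**The concern.** A stopping boundary and a safety conclusion answer different questions. The boundary asks whether the DLTs seen so far are too many to go on enrolling. The conclusion asks which true DLT rates the data can rule out. Section 6 answers the second question with the first: an observed proportion of 33% or less is enough for the label *safe*, whatever the uncertainty in that proportion.

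With about 12 patients the uncertainty is large. Taken at its word, the plan would call the regimen safe after 3 DLTs in 12, although that result is compatible with a true rate above one half. What is at stake is how a reader may interpret a trial that was simply not stopped.

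**Working it through.** **Inputs.** Threshold 33% and the first-three exception (Section 6); N = 12 (Section 13.3); two DLTs in the first 6 patients at 300 mg (Section 5.1). The plan derives no safety figure, so there is none to reproduce. The 95% level is my assumption.

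**What the rule allows at 12 patients.** 4/12 = 33.3%, which is above 0.33 but not above 1/3. Read literally, the rule allows up to 3 DLTs; read as one third, it allows 4.

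**What each allowed result excludes.** The exact upper limit U solves P(X ≤ x | 12, U) = α, with α = 0.05 one-sided or 0.025 two-sided. For x = 0 this is U = 1 − α^(1/12): 1 − 0.05^(1/12) = 22.1% and 1 − 0.025^(1/12) = 26.5%.

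| DLTs of 12 | Observed | Exact two-sided 95% interval | One-sided 95% upper limit | Excludes 33%? |
|---|---|---|---|---|
| 0 | 0% | 0–26% | 22.1% | yes |
| 1 | 8.3% | 0.2–38% | 33.9% | no, borderline |
| 2 | 16.7% | 2–48% | 43.8% | no |
| 3 | 25% | 5–57% | 52.7% | no |
| 4 (one-third reading only) | 33.3% | 10–65% | 60.9% | no |

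The 1-of-12 case: P(X ≤ 1 | 12, 0.33) = 0.67^12 + 12 × 0.33 × 0.67^11 = 0.0082 + 0.0484 ≈ 0.0565, just above 0.05. Other conventions do exclude 33% here: one-sided 90% exact (28.8%), and one-sided 95% Wilson (30.1%), mid-P (29.9%) and Jeffreys (28.3%). Two-sided 95% Wilson (35.4%) does not. If replacement brought the treated total to 13, 1 DLT would just exclude 33% at one-sided 95% exact. Results of 2 or 3 DLTs in 12 fail under every method tried.

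**How the boundary performs.** Let A_k(x) be the probability of still accruing after k patients with x DLTs, at true rate p. Then A_k(x) = (1 − p)·A_{k−1}(x) + p·A_{k−1}(x − 1) if x is allowed at k, and 0 otherwise. The allowed maxima are:

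- Literal 33%: 1 for k = 1–6 (k = 1–3 by the exception), 2 for k = 7–9, 3 for k = 10–12.
- One third: 1 for k = 1–5, 2 for k = 6–8, 3 for k = 9–11, 4 for k = 12.

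Summing A_12(x) over x gives the chance of completing 12 patients within the rule, assuming each DLT is known before the next patient enters:

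| True DLT rate | Literal 33% | One third | One third plus Section 5.1 rule |
|---|---|---|---|
| 33% | 25% | 33% | 29% |
| 40% | 13% | 19% | 16% |
| 50% | 4% | 7% | 6% |

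Under the literal reading the Section 5.1 rule changes nothing if all of the first 6 patients are at 300 mg, because both rules then stop at the second DLT. With no monitoring and a single look at 12, P(X ≤ 3) would be 40%, 23% and 7% at the same three rates. Section 6 monitors toxicity continuously, so the monitored figures are the relevant ones.

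**The case against.** The strongest reply is that the sentence sits inside a stopping rule. Section 6 introduces it with a promise of stopping rules, the next sentence applies the same 33% to accrual, and the section concerns dose modification, not analysis. On the literal reading the rule stops about 75%, 87% and 96% of trials at true rates of 33%, 40% and 50%. All of this stands: the boundary is sound in kind and protects patients. It does not rescue the word *safe*, which is a conclusion that the accrual rule does not need.

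A second reply is that wide intervals are unavoidable with 12 patients in a trial that Section 11 calls exploratory. That is true, and it is a reason not to fix the conclusion in advance. No larger sample is asked for.

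A reader might infer more than the documents support:

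- **That Objective 6 will be reported as met on the 33% test.** No section ties 33% to the reporting of that objective; 5.6, 11 and 13.5.4 do not mention it.
- **That follow-on trials depend on this label.** Sections 1 and 11 make them depend on changes at the tumor. Section 2.4.3 links later work to safety data only for patients enrolled soon after PD-1 antibody, and does not cite 33%.
- **That only 0 DLTs could ever exclude 33%.** This holds at 95% exact confidence with 12 treated, not under every method or with 13 treated.
- **That incomplete follow-up dilutes the safety conclusion.** The denominator of patients accrued belongs to the accrual sentence. The sentence containing *safe* refers to participants, and 13.6.1 counts everyone from first treatment.

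**Conclusion.** The point holds as a matter of what may be concluded. Section 6 states a criterion for calling the regimen safe that is satisfied by results, 2 or 3 DLTs in 12, whose exact 95% intervals reach 48% and 57%; on the one-third reading 4 in 12 also qualifies, reaching 65%. Nothing elsewhere in the plan supplies an interval or an acceptable true rate to temper it.

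The consequence is moderate. The boundary itself makes completion unlikely at high true rates, and the primary analysis and sample size are unaffected. The intervals assume 12 treated patients, a common DLT probability and fixed-sample exact limits. The completion probabilities also assume that DLTs are known immediately. If DLTs emerge late, accrual could continue longer than those figures suggest.

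**What to change.** 1. **Section 6:** reword the sentence so that it says only that accrual is not closed under this rule while the threshold is not exceeded, and drop the statement that the regimen is considered safe.
2. **Section 13.5.4:** add wording such as: *The proportion of all treated patients with a treatment-related DLT is reported with an exact 95% confidence interval. A proportion at or below 33% is not in itself a conclusion of safety.* Counts by INCB024360 dose may be listed descriptively. The plan gives no dose-group sizes, so intervals by dose are not requested.
3. **For the sponsor to reconcile:** whether 33% means 0.33 or one third, which changes the limit at 6, 9 and 12 patients; how the Section 6 and Section 5.1 rules fit together; and the numerator, since Sections 5.2 and 6 define DLTs regardless of attribution while the 33% rule counts treatment-related ones. No change to the stopping threshold is proposed here.

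The cost is a few lines of text. The downside is a less favourable safety statement.
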